10.2. Sample Size Determination

It is planned to enrol 12 subjects in Part A and 128 subjects in Part B. No formal sample size calculation has been performed. A study of 12 subjects in Part A and 128 subjects in Part B are considered to be sufficient to meet the objectives of the study.

10.3. Statistical Analysis Plan

A Statistical Analysis Plan (SAP) will be prepared after finalising the Protocol and before database lock. The specifications in this document will detail the implementation of all the planned statistical analyses in accordance with the principal features stated in the Protocol. The SAP will provide full details of the analyses, data displays, and algorithms to be used for data derivation. Any deviation from the original SAP will be described in the Clinical Study Report.

10.4. Analysis Sets

A subject who withdraws prior to the last planned observation in the study period will be included in the analyses up to the time of discontinuation.

10.4.1. Safety Set

10.4.1.1. Part A

The Safety Set will consist of all subjects who received a dose of the IMP (KLS-GABA or KLS).

10.4.1.2. Part B

The Safety Set will consist of all subjects who received a dose of the IMP (KLS, KLS-GABA, gabapentin, or Placebo).

10.4.2. Pharmacokinetic Set

10.4.2.1. Part A

The PK Set will consist of all subjects who received a dose of the IMP (KLS-GABA or gabapentin) and have evaluable PK data.

10.4.2.2. Part B

The PK Set will consist of all subjects who received a dose of the IMP (KLS, KLS-GABA, gabapentin, or placebo) and have evaluable PK data.

10.4.3. Pharmacodynamic Set

10.4.3.1. Part A

The PD set is not required for Part A of this study.

10.4.3.2. Part B

The PD set will consist of all randomised subjects who received a dose of randomised therapy. Patients will be analysed according to their actual treatment received (a per protocol analysis set). The analyses of efficacy endpoints will use the PD set.

10.5. Statistical Analysis

Separate analyses will be provided for Part A and Part B study.

Appropriate descriptive statistics will be produced, according to the nature of the variable. For continuous data n, mean, standard deviation (SD), median and range (minimum and maximum) will be presented. For categorical data, frequency distributions and percentages will be presented.

All the data collected and derived in the study will be presented in subject data listings.

Statistical analyses will be performed using SAS 9.4.

10.5.1. Subject Disposition and Characteristics

A description of subject disposition will be provided. It will include a summary of the number and percentage of subjects entered into the study, enrolled in the study, and treated as well as number and percentage of subjects completing the study, or discontinuing (overall and by reason for discontinuation). All entered subjects will be accounted for in this summary of disposition. A summary of all protocol deviations will be provided.

Demographic and baseline characteristics, medical history, concomitant medication and treatment compliance will be summarised for all subjects in the Safety Set by treatment.

10.5.2. Safety Statistical Analysis

Safety assessments will include standard laboratory safety evaluations (haematology, biochemistry, coagulation, and urinalysis), vital signs (blood pressure, heart rate and oral temperature), physical examinations, 12-lead ECG and AE monitoring.

10.5.2.1. Adverse Events

All AEs will be listed according to SOC and preferred term (PT) assigned to the event using Medical Dictionary for Regulatory Activities (MedDRA; highest version). Number and percentage of subjects who experienced any AEs will be summarised by treatment. Furthermore, AEs will be summarised by causality and the maximum intensity. Any SAEs and/or AEs that led to withdrawal will be listed.

10.5.2.2. Clinical Laboratory Evaluations

Clinical Laboratory evaluation results will be listed and compared to laboratory reference ranges, with those values outside of the applicable range flagged as high (H) or low (L). The

quantitative laboratory data will be summarised using descriptive statistics for each parameter by treatment and time. Urinalysis data will be listed only. A summary of subjects reporting an abnormal value will be reported.

10.5.2.3. Vital Signs

Vital signs (supine systolic blood pressure, diastolic blood pressure, heart rate and body temperature) will be listed for individual subjects. Summary statistics will be calculated for each parameter by treatment and time.

10.5.2.4. 12-Lead Electrocardiogram

Standard 12-lead ECG parameters (RR, PR, QRS, QTcF intervals and HR) will be listed for individual subjects. Out-of-range ECG values will be flagged as high (H) or low (L). Summary statistics will be calculated for each parameter by treatment and time. Where multiple values are recorded at a timepoint for a subject, the mean of the values will be used in the summary statistics.

10.5.2.5. Physical Examination

Physical examination data will be listed for individual subjects. Summary statistics will be calculated for each parameter by treatment and time.

10.5.3. Pharmacokinetic Statistical Analysis

KLS, KLS-GABA and gabapentin concentrations and parameters will be summarised using all subjects in the PK Set. Full details of the PK analysis will be included in the PK Analysis Plan.

10.5.3.1. Derivation of Pharmacokinetic Parameters (Part A only)

Pharmacokinetic parameters will be derived from plasma concentration data of ketoprofen when given alone (KLS) and ketoprofen and gabapentin when given in combination (KLS-GABA) by noncompartmental analysis. The PK parameters derived to assess the single dose PK of KLS and KLS-GABA are shown in [Table 5](#).

Table 5: Pharmacokinetic Parameters (Part A)

Abbreviation	Definition
C_{\max}	Maximum plasma concentration
t_{\max}	Time of maximum plasma concentration
AUC_{0-12h}	Area under the plasma concentration-time curve from zero to 12 hours postdose
AUC_{0-24h}	Area under the plasma concentration-time curve from zero to 24 hours postdose
AUC_{0-36h}	Area under the plasma concentration-time curve from zero to 36 hours postdose
AUC_{0-48h}	Area under the plasma concentration-time curve from zero to 48 hours postdose
AUC_{0-t}	Area under the plasma concentration-time curve from zero to the last quantifiable concentration
$AUC_{0-\infty}$	Area under the plasma concentration-time curve from zero to infinity
$t_{1/2}$	Apparent terminal half-life

10.5.3.2. Statistical Analysis of Pharmacokinetic Parameters (Part A only)

The ketoprofen and gabapentin PK parameters AUC_{0-t} , AUC_{0-12h} , AUC_{0-24h} , AUC_{0-36h} , AUC_{0-48h} , $AUC_{0-\infty}$ and $t_{1/2}$ will be generated using noncompartmental methods. C_{\max} will be determined directly from the data.

10.5.4. Pharmacodynamic Statistical Analysis

Summaries and descriptive statistics will be produced for each PD parameter. This includes Scores (VAS or NRS) / Area measured (cm^2) for each treatment and timepoint, along with change from baseline in Score / Area.

Mixed Model Repeated Measures (MMRM) will be fit to data for each PD parameter using two groups of models. Group 1 will assess longitudinal changes in Scores / Area against baseline. Group 2 will assess differences in Scores / Area between treatments for each timepoint.

10.5.4.1. Descriptive statistics

Descriptive statistics will be produced for each PD parameter. Separate tables will be produced that report summary statistics for Scores (VAS or NRS) and Area measured (cm^2) for each PD parameter.

Corresponding figures will be produced for each PD parameter, separately for each patient and combined for all patients in a treatment group. Figures that summarise overall mean/median Score/Area across patients will be produced combining all treatment groups.

10.5.4.2. Modelling

Two separate sets models will be fit to the data. Individual models will be fit per treatment group to assess means and change from baseline in score and area for each PD parameter. Combined models will be fit using all treatment groups to assess differences in means and change from baseline in score/area against placebo.

Model Group 1:

The MMRM model will contain a term for timepoint and will contain baseline Score / Area as a covariate and subject as a random effect. An unstructured covariance matrix will be assumed.

If the fit of the unstructured covariance structure fails to converge, the following covariance structures will be tried in order until convergence is reached: toeplitz with heterogeneity, autoregressive with heterogeneity, toeplitz, and autoregressive.

Least squares (LS) means will be reported for each visit along with corresponding 95% confidence intervals (CIs).

The model will be fit separately for each treatment group, for the following dependent variables:

- A) Score / Area for each PD parameter
- B) Change in score / Area for each PD parameter

Model Group 2:

The MMRM model will contain terms for randomised treatment group and timepoint and will contain baseline Score / Area as a covariate and subject as a random effect. An unstructured covariance matrix will be assumed.

If the fit of the unstructured covariance structure fails to converge, the following covariance structures will be tried in order until convergence is reached: toeplitz with heterogeneity, autoregressive with heterogeneity, toeplitz, and autoregressive.

Least squares (LS) means will be reported by visit for each randomised treatment group; the difference in LS means between each dose arm and placebo will be presented along with corresponding 95% CIs.

10.5.5. Pharmacokinetic/Pharmacodynamic Statistical Analysis

Further details of the planned PK/PD correlation analysis will be provided in the SAP.

10.6. Handling of Missing or Incomplete Data

Unrecorded values will be treated as missing. Depending on the extent of the missing values, further investigation may be made into sensitivity of the analysis results to the method(s) specified.

11. DATA HANDLING AND RECORD KEEPING

11.1. Collection of Data

Data collected from each completed subject will be recorded on source documents, which will be entered into an eCRF. The Investigator is responsible for ensuring that all sections of the eCRF are completed correctly and that entries can be verified against the source documents. If certain data are not available or not applicable this will be indicated as such within the appropriate area of the eCRF.

Screening failures (subjects who signed consent to take part in the study but were not dosed) will not be entered into the clinical study database.

Data produced by automatic devices with original printouts (i.e., clinical laboratory evaluation results, ECG traces) will be attached to the source documents. Clinical laboratory parameters will be provided in laboratory printouts which are to be signed by the Investigator. Comments on all clinically significant abnormal values will be provided and documented by the Investigator or appropriately recorded within the eCRF.

Adverse Events and Medical History will be reported by the MedDRA SOC and PT; the latest version will be applied to all terms. All Medical History and AEs will be included in the data listings. Furthermore, all Prior Medications and Concomitant Medications will be reported using the WHODRUG categorization; the latest version will be applied to all terms.

All Prior Medications and Concomitant Medications will be summarised within the data listings.

Any missing, implausible, or inconsistent recordings within the eCRFs will be referred to the Investigator using data query validation procedures; will be documented and resolved for each individual subject before database lock is declared.

All processes pertaining to the Data Management activities will be detailed within the Data Management Plan.

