3.2. Part B

Part B is a randomised, double-blind, placebo-controlled parallel group study to investigate single oral doses of KLS alone or KLS-GABA compared to 300 mg gabapentin alone or placebo, in healthy male subjects using the ID capsaicin model.

[figure not shown]

Figure 5: Study Design (Part B)

It is planned to enrol 128 subjects randomised evenly to 8 possible treatments; subjects will receive either KLS alone, KLS-GABA, 300 mg gabapentin or placebo.

The planned treatments are:

- KLS alone (40 mg, 80 mg or 160 mg)
- KLS-GABA (40 mg-17mg, 80 mg-34 mg, or 160 mg-68 mg)
- Gabapentin* (300 mg)
- Placebo

* Product commercialised in Italy: Neurontin 300 mg hard capsules.

Subjects will be required to attend the CRU for a screening visit within 28 days prior to dosing to ensure they meet the inclusion/exclusion criteria and are in good general health ([Section 6](#)).

Following initial screening, subjects will be required to attend the CRU for an additional screening visit at least 7 days prior to first dosing to assess their response to capsaicin and familiarise them in the pain measurements. Subjects will receive a single ID administration of 100 µg capsaicin into a novel site on the volar surface of the forearm. Prior to and 15 minutes after administration of capsaicin, measurements of pain, hyperalgesia, allodynia and AF will be performed according to the procedures described in [Section 9](#). In order for the subjects to be eligible, they must be able to tolerate the injection and also demonstrate a sufficient response, defined as an area of hyperalgesia $\geq 15\text{cm}^2$ 15 minutes after the injection.

Subjects will be admitted to the CRU on Day -1 for collection of baseline safety assessments, pain measurements and to complete the ID capsaicin model (see [Appendix 2](#)). Subjects will receive a single 100 µg capsaicin injection into a novel site on the volar surface of the forearm.

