7.5.3. Reporting Procedures and Requirements

7.5.3.1. Adverse Events

Events occurring from the time of signed informed consent will be considered as AEs. A baseline AE assessment will occur after Screening. All AEs between screening to the follow-up visit will be recorded in source and eCRF, whether or not considered study medication related. All AEs that are possibly or probably related to study medication will be followed until resolution or database lock, whichever occurs first. Also, the sign, symptom, or disease present before the baseline AE assessment are only considered AEs if they worsen after this point. Any AEs already documented at a previous assessment and designated as ongoing should be reviewed at subsequent visits as necessary. If these have resolved, this should be documented. Changes in intensity or frequency of AEs should be recorded as separate events (i.e., a new record started). The Investigator should report all AEs on the AE page(s) of the eCRF and source documents, regardless of seriousness, severity, and causality. Whenever possible, an AE will be reported using a diagnostic term, (e.g., "common cold" or "upper respiratory infection" rather than "runny nose, cough, mild fever") and should be described with the attributes described in [Section 7.5.1.1](#).

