4.2. Analysis Sets (Part B)

4.2.1. Intent-to-Treat Set (Part B)

The ITT Set will be defined as all subjects randomized. A subject's randomized treatment will be used for analysis regardless of the actual treatment received. ITT Set will be used for disposition and demographic analysis.

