6. ANALYSIS METHODS

6.1. Participant Disposition

Disposition will be summarized descriptively using counts and percentages for All Patients separately for Part A and Part B. Subjects from Part A will be analysed by planned treatment sequence and overall. Subjects in the Part B will be analysed by planned treatment and in overall. The number and percentage of subjects entered into the study, enrolled in the study, randomized, and treated as well as number and percentage of subjects completed the study will be presented, together with number and percentage of subjects who prematurely discontinued from the study along with reasons for study discontinuation.

A listing of subject disposition status will be provided separately for Part A and Part B. The number of subjects in each analysis set will be summarized descriptively by treatment with counts and percentages separately Part A and Part B.

A listing of subject's inclusion to analysis sets will be provided separately for Part A and Part B. A subject's eligibility with inclusion/exclusion criteria completions or violations will be listed separately for Part A and Part B.

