6.3. Demographic and Baseline Characteristics

Demographic data and baseline characteristics, including age, gender, ethnicity, height, body weight and BMI will be summarised.

Demographic data will include gender, age and ethnicity. Baseline characteristics will include body weight, height and BMI.

Demographics and baseline characteristics will be summarized for all subjects overall and by treatment sequence (Part A) or treatment (Part B). Summary statistics will be generated for all continuous variables (i.e., age and weight, height and BMI) and the number and percentage of subjects within each category will be presented for all categorical variables (i.e., gender, race and ethnicity). The summary results for Part A and Part B will be based on the ITT Set.

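### Protocol 11.1 keeps every consented but undosed subject out of the clinical database, which contradicts the all-randomised ITT Set, the disposition counts and the rule that all adverse events from screening go into the eCRF.

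*Protocol*

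**What the plan says.** Protocol 11.1 (Collection of Data) sets the rule: "Screening failures (subjects who signed consent to take part in the study but were not dosed) will not be entered into the clinical study database". The same section says that all AEs will appear in the data listings.

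Other sections assume that undosed subjects are in the data:

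- **ITT Set.** SAP 4.2.1 (Part B) reads "The ITT Set will be defined as all subjects randomized" and adds "ITT Set will be used for disposition and demographic analysis". SAP 4.1.1 says the same for Part A. On demographics, SAP 6.3 says "The summary results for Part A and Part B will be based on the ITT Set". Medical history (SAP 6.4) also uses this set.
- **Disposition.** SAP 6.1 asks for separate counts: "The number and percentage of subjects entered into the study, enrolled in the study, randomized, and treated". Protocol 10.5.1 says "All entered subjects will be accounted for in this summary of disposition".
- **Adverse events.** Protocol 7.5.3.1 counts events from signed consent and says "All AEs between screening to the follow-up visit will be recorded in source and eCRF". Protocol 7.5.5 allows no exemption. Protocol 7.5.3.2 sends SAEs from consent to source and electronic data capture. Protocol 7.5.1.1 lets AEs include pre-treatment events caused by procedures the protocol requires.
- **Capsaicin before dosing.** Protocol 3.2 gives Part B subjects capsaicin at an "additional screening visit at least 7 days prior to first dosing to assess their response to capsaicin", and again on Day -1.

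SAP Section 8 lists one departure from the protocol, the change of the Part B primary endpoint. It does not mention this conflict.

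**The concern.** A screening failure is normally someone who was never randomised. Protocol 11.1 draws the line at dosing, so the label also covers a subject who passed screening, was randomised and then received no dose. A set defined as all randomised cannot be filled from a database that holds only the dosed.

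The second consequence is specific to Part B. The capsaicin injection is a study procedure, and tolerating it at screening is an inclusion criterion (Protocol 6.1.2, item 9). A subject who does not tolerate it is not dosed, so under 11.1 he has no database record. The gap is therefore selective: it removes those who tolerated the injection worst. Protocol 3.3 describes the injection as safe and well tolerated, and the trial's AE listings could not fairly bear on that statement.

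Site staff also cannot obey both instructions. For an undosed subject with an AE, 7.5.3.1 and 7.5.5 require eCRF entry and 11.1 forbids database entry.

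**Working it through.** The plan gives no figure to reproduce, and no error-rate or sample-size formula applies. The check sets the rules side by side.

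**1. Set membership.** Let R be the subjects randomised and D the subjects dosed. Under the plan only randomised subjects are dosed, so D lies within R.

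- Database under Protocol 11.1: D only.
- ITT Set under SAP 4.1.1 and 4.2.1: R.
- ITT Set that can be drawn from the database: R ∩ D = D.
- Safety Set under SAP 4.1.2 and 4.2.2: D.

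From database records alone, ITT and Safety therefore have the same members, and defining both serves no purpose.

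**2. Disposition.** SAP 6.1 wants a randomised count and a treated count. With only D in the database, the randomised row cannot exceed the treated row.

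**3. Can R and D differ?** Yes. Protocol 10.1 does not tie randomisation to the moment of dosing. Under Protocol 3.6, meeting any study stopping criterion, one of which is a positive SARS-CoV-2 test, halts dosing in all subjects. Anyone randomised and waiting at that point would be in R but not in D.

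**4. Capsaicin exposure in undosed Part B subjects.**

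| Point at which the subject leaves | Capsaicin injections received | Database record under 11.1 |
|---|---|---|
| First screening visit | 0 | None |
| After the injection at the additional screening visit (not tolerated, or hyperalgesia area below 15 cm²) | 1 | None |
| After the Day -1 injection, before the Day 1 dose | 2 | None |

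In the last two rows, any AE after the injection is due in the eCRF under 7.5.3.1 and 7.5.5 and excluded under 11.1. SAP 6.6.1 also says that all AE data will be listed.

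**5. What does not change.** The PD Set (SAP 4.2.4) requires a dose and a completed capsaicin injection. The Safety Set requires a dose. AE summaries (SAP 6.6.1) count events with onset or worsening on or after study drug. None of these involves an undosed subject.

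**The case against.** The strongest reply is that the wording in 11.1 is merely loose. A randomised subject has passed screening, so the heading word does not naturally describe him, and few such subjects are likely. Randomisation requires all criteria to be met, including a negative Day -1 SARS-CoV-2 test, and dosing follows in the unit the next morning. This stands as a limit on size. It does not remove the conflict, because the parenthesis is an explicit definition.

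A reader might infer that the ITT Set and disposition cannot be built at all. The documents do not support that. The randomisation scheme and numbers (Protocol 10.1) identify who was randomised. Protocol 13.3 has the research unit keep a record of all subjects screened, and requires the main reason to be recorded when a subject receives no treatment. Membership and counts can be assembled from these, outside the database. Demographics and medical history for undosed subjects have no such stated route.

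A reader might also infer that AEs after capsaicin are lost. They are not plainly discarded. They stay in source, SAEs go on the SAE form, and events in subjects who are later dosed are kept. The instructions conflict; neither is stated to prevail.

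Two further points have some force. The word entered in Protocol 10.5.1 is not defined, and 7.5.1.1 uses entering the study to mean passing screening. Leaving ordinary screen failures out of disposition may therefore not breach 10.5.1, and the conflict with SAP 4.2.1 and 6.1 is the firmer one. Also, the eCRF and the Data Management Plan are not available here, and either may already provide pages for undosed subjects.

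**Conclusion.** The contradiction is real and minor. If 11.1 is applied literally, ITT drawn from the database collapses to the dosed subjects, and AEs after capsaicin in Part B subjects never dosed are missing from the database and AE listings. The damage is confined to ITT descriptive tables, disposition and AE listings. No efficacy estimate and no treatment-emergent AE summary changes.

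The number affected cannot be derived. A reader might try to size it by assuming that 20% to 50% of capsaicin-screened subjects are not dosed: 128/(1 − 0.2) = 160 exposed, 32 of them undosed; 128/(1 − 0.5) = 256 exposed, 128 undosed. Those rates are assumptions with no source in the documents. The results count people exposed rather than events missed, and they say nothing about randomised-but-undosed subjects. They should not be quoted as the size of the problem.

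The conclusion assumes that 11.1 is followed as written and that no unseen data-management document overrides it.

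**What to change.** In Protocol 11.1, define a screening failure as a subject who consented but was not randomised. Then:

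- enter every randomised subject in the database, dosed or not;
- for any undosed subject given capsaicin, enter a minimal record of demographics, reason not dosed, capsaicin exposure, and AEs and SAEs;
- check that 11.1 then agrees with Protocol 7.5.3.1, 7.5.3.2 and 7.5.5 and with SAP 4.1.1, 4.2.1 and 6.1, and state in 10.5.1 what entered means.

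The cost is a short protocol wording change, a short eCRF form for undosed subjects and modest extra data entry. No procedure and no analysis model changes.
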